2.3.3 Additional Studies

An open label, self-controlled study (SHR0302-105) evaluating drug interaction potential between SHR0302 and methotrexate (MTX) in subjects with rheumatoid arthritis was recently completed. Subjects were to take MTX 10 mg once daily on Day 1 and Day 8, and SHR0302 10 mg once daily on Days 3 to Day 8. Overall, 15 subjects were enrolled. A total of 18 adverse events were reported in 8 of 15 subjects (53.3%). Of the 18 adverse events, 3 subjects (20.0%) reported 5 adverse events after SHR0302 alone, 4 subjects (26.7%) reported 5 adverse events after MTX alone, and 3 subjects (20.0%) reported 8 adverse events after MTX and SHR0302 in combination. The adverse events reported in subjects given SHR0302 alone included headache, back pain, fever, constipation and tachycardia each in 1 subject (6.7%). The adverse events reported by the subjects after MTX and SHR0302 in combination included anemia, upper respiratory tract infection, urinary tract infection, elevated blood triglycerides, elevated aspartate aminotransferase, positive urine leukocytes and tachycardia each in 1 subject (6.7%). No serious adverse events were reported, and no subjects withdrew prematurely due to adverse event.

Ongoing Studies

Two studies of SHR0302 as an oral treatment of inflammatory bowel disease are ongoing. RSJ10101 is a phase 2, randomized, placebo-controlled, double-blind, 4 arm, dose-ranging study to evaluate the efficacy and safety of SHR0302 compared to placebo in adults with moderate to severe, active ulcerative colitis. Treatment groups include 3 different doses of SHR0302 (4mg QD, 8mg QD, 4mg BID) or placebo, with 1:1:1:1 randomization. The study consists of an 8-week blinded treatment phase, followed by an 8-week of blinded, active extension phase. Planned enrollment is 152 across China, Ukraine, United States, and Poland. RSJ10201 is a phase 2, randomized, placebo-controlled, double-blind, four arms dose-ranging study to evaluate the efficacy and safety of SHR0302 compared to placebo in adults with moderate to severe, active Crohn's disease. Treatment groups include 3 different doses of SHR0302 (4mg QD, 8mg QD, 4mg BID) or placebo, with 1:1:1:1 randomization. The study consists of a 12-week blinded treatment phase, followed by a 12-week of blinded, active extension phase. Planned enrollment is 144 across China, Ukraine, United States, and Poland. Analysis of blinded data from these two ongoing studies in IBD (RSJ10101 and RSJ10201) as of October 19, 2019 has been performed. Based on this analysis, 39 subjects were estimated to be exposed to SHR0302 in these two clinical trials. One SAE was reported as colitis ulcerative and the other one was synovitis. The latter SAE was unblinded and confirmed to be on SHR0302.

Overall, the reported safety data were in line with the known and expected safety profile of SHR0302.

Finally, two additional studies of SHR0302 recently started, for which no data is currently available. RSJ10303 is a phase 2 study in China of SHR0302 in atopic dermatitis. The study is a randomized, double-blind, and placebo-controlled, evaluating the efficacy and safety of SHR0302 4mg QD, SHR0302 8mg QD, or placebo in adult patients with moderate to severe atopic dermatitis. RSJ10411 is a phase 1, vehicle-controlled study in Australia and China to evaluate the safety and pharmacokinetics of SHR0302 base ointment at single dose and multiple dose in healthy adult subjects.

2.4 Rationale for Development

Since the first demonstration of the clinical efficacy of JAK inhibitors for the treatment of eczema, which utilized a topical formulation of tofacitinib for the treatment of atopic dermatitis, numerous oral JAK inhibitors and several other topical JAK inhibitors have also demonstrated efficacy in eczema. We are pursuing the development of ARQ-252 cream as a topical JAK1-selective inhibitor for the treatment of hand eczema, planning to take advantage of the efficacy of this class of agents in this disease, while minimizing systemic exposure and undesirable side effects. Nonclinical and systemic clinical data with SHR0302 to date are supportive of this plan.

The above data indicate that topical ARQ-252 could provide an important addition to the dermatologist's approach for treating hand eczema.

2.4.1 Dose Selection

ARQ-252 cream 0.3% was selected as the high clinical dose because this dose remains in solution when stored at controlled room temperature.

In Cohort 1 of this study, ARQ-252 cream 0.3% will be applied QD to approximately 4% BSA in subjects with hand eczema. It is well known that cutaneous disease states can alter drug permeability as compared to normal human skin. Since eczematous skin may have different drug permeability characteristics than normal skin ([Ortiz 2009](#); [Halling-Overgaard 2017](#)), this study is planned in patients with hand eczema rather than healthy volunteers. Administration of ARQ-252 cream 0.3% once-daily to approximately 4% of BSA at an application rate of approximately 0.75 mg/cm² would result in 1.5 mg of total SHR0302 being absorbed per day, assuming 100% absorption of applied drug, an amount well covered by the oral MAD study discussed previously ([Section 2.3.1](#)). In the oral MAD, daily doses of 2 to 10 mg resulted in signals for thyroid effects (elevated TSH, decreased free T4), mild LFT abnormalities, and a few urinary tract infections. These are all easily monitored, and skin absorption is very likely to be only a small fraction of 100%. Moreover, in the Phase 2 RA study, mean WBC, neutrophils, lymphocyte, HGB, platelet count, liver function and kidney function remained in the normal range in all SHR0302 treatment groups.

Following a review of safety and PK data from Phase 1 (Cohort 1) of this study, Phase 2b (Cohort 2) can commence. Phase 2b (Cohort 2) is a parallel group, double blind, vehicle-controlled cohort in which subjects with chronic hand eczema will be randomized to ARQ-252 cream 0.3% QD, ARQ-252 cream 0.3% BID, ARQ-252 cream 0.1% QD, vehicle cream BID or vehicle cream QD.

2.4.2 Risks and/or Benefits to Subjects

The potential risks of ARQ-252 cream stem from what is known about the safety of the oral form of this drug, and risks associated with the JAK inhibitor mechanism. These risks include serious infections, other infections (e.g., upper respiratory tract infections, opportunistic infections, herpes), anemia, lymphopenia, natural killer (NK) cell reduction, neutropenia, platelet elevations or reductions, malignancy and lymphoproliferative disorders, gastrointestinal perforations, liver function abnormalities, thyroid function abnormalities, lipid elevation, serum creatinine elevations, creatine phosphokinase elevations, thrombosis, nausea, diarrhea, headache, and hypertension. In general, topical delivery is expected to carry lower risk than oral administration at therapeutic doses to the degree that systemic exposure is reduced. Previous nonclinical research showed that the active ingredient in ARQ-252 can harm fetal development. Please refer to the Investigator's Brochure for detailed information.

Phase 1 (Cohort 1)

Subjects in Cohort 1 subjects may see an improvement in their hand eczema, although the study duration of 2 weeks may limit this possibility.

Phase 2b (Cohort 2)

Subjects randomized to active treatment in Cohort 2 may see an improvement in their hand eczema with the use of ARQ-252 cream. Those receiving vehicle cream may also see improvement related to the moisturizing properties of the vehicle

The safety monitoring practices employed in this protocol (i.e., physical examinations, application site reaction assessments, hematology, serum chemistry, TSH, T4, urinalysis, ECG, and AE questioning) are adequate to protect the subjects' safety and should detect expected AEs.

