ACR70 Percentage (%)	0.0	4.0	4.2	13.0	12.5	26.7
(95% CI)	(0.0, 9.5)	(0.1, 20.4)	(0.1, 21.1)	(2.8, 33.6)	(4.2, 26.8)	(14.6, 41.9)
% difference from placebo	-	4.0	4.2	13.0	12.5	26.7
(95% CI)		(-6.0, 19.5)	(-5.8, 20.2)	(0.4, 32.1)	(0.8, 26.1)	(12.4, 41.0)
P value	-	0.2440	0.1797	0.0267	0.0284	0.0007

Investigator's Brochure, Edition 1.0, Feb 2020.

Preliminary safety results include:

- SHR0302 was generally safe and well tolerated. A higher frequency of infections was observed in SHR0302-treated subjects, particularly in the 8mg group. The most common infections included upper respiratory tract infections and urinary tract infections.
- Mean WBC, neutrophils, lymphocyte, HGB, platelet count, serum lipid level, liver function, kidney function, and thyroid function parameters remained in the normal range in all SHR0302 treatment groups.
- Mean platelet count did not increase during the study.
- Increases in LDL, HDL, total cholesterol and triglycerides were observed. However, LDL-to-HDL remained stable.
- Increase in mean serum creatine kinase (CK) was observed in patients treated with SHR0302 versus placebo but was within normal range. CK-MB remained stable.
- Most of the reported abnormal laboratory results were classified as CTCAE grade 1 or 2. CTCAE grade 3 events included: 1 case of increased alanine aminotransferase (4 mg), 1 case of decreased neutrophils (8 mg), 1 case of decreased lymphocytes (4 mg) and 1 case of anemia (8 mg).
- From Baseline through Week 12, the most common AEs ($\geq 5\%$ across pooled SHR0302 groups) included upper respiratory infection, hyperlipidemia, swollen joint, urinary tract infection, hypercholesterolemia, joint pain, and cough. From Baseline to Week 12, other TEAEs occurring at rates $\geq 5\%$ in individual SHR0302 groups (although $< 5\%$ across pooled SHR0302 groups) included hypothyroidism, anemia, liver dysfunction (although placebo group had highest rate), elevated serum creatine phosphokinase, diarrhea, headache, hematuria, abdominal discomfort, urine protein detection, blood in urine, elevated blood lactic dehydrogenase, and upper abdominal pain. Additional common AEs ($\geq 5\%$ across pooled SHR0302) seen from Baseline through Week 24 included elevated serum creatine phosphokinase, anemia, and hypothyroidism.

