5.1.6 Laboratory Tests

All tests listed in Table 3 below will be performed according to the Schedule of Visits and Assessments (Section 1.3) unless otherwise noted. The collection of specimens will be in a non-fasting state (no food restrictions). In addition, laboratory safety tests may be performed at various unscheduled time points, if deemed necessary by the Investigator.

Table 3. Laboratory Tests

Hematology	Serum Chemistry

 • Hemoglobin • Hematocrit • Total and differential leukocyte count • Red blood cell count with indices and morphology • Platelet count • Reticulocyte count¹ 	
 • Blood Urea Nitrogen • Bilirubin (total and direct) • Alkaline phosphatase • Aspartate aminotransferase • Alanine aminotransferase • Albumin • Sodium • Potassium • Chloride • Glucose • Creatinine • Creatine kinase
Urinalysis	Additional Tests

 • pH • Specific gravity • Protein² • Glucose • Ketones • Bilirubin • Blood² • Nitrite² • Urobilinogen • Leukocyte esterase² 	
 • Thyroid Stimulating Hormone T4 (TSH/T4) • Urine pregnancy test³ (for females of childbearing potential only) • Serum pregnancy test (hCG)⁴ • Follicle-stimulating Hormone (FSH) ⁵ • Pharmacokinetic (PK) assessments

¹ If red blood cell count, hemoglobin or hematocrit values are below the lower limit of normal, reticulocyte count will be performed

² If urinalysis is positive for protein, blood, nitrite and/or leukocyte esterase, a microscopic examination (for red blood cells, white blood cells, bacteria, casts, and epithelial cells) will be performed.

³ Cohort 1: At Baseline, Day 8, Day 15 and Day 22 for FOCBP only. Cohort 2: At Baseline, Week 4, 8, 12 and 13 for FOCBP only.

⁴ At screening only for FOCBP.

⁵ If indicated to confirm post-menopausal status

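### Lipid elevation is a listed risk of ARQ-252, but no lipid test is scheduled, so the monitoring statement and the laboratory panel need to be reconciled

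*Protocol*

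**What the plan says.** **The risk.** Protocol Section 2.4.2 draws its list of potential risks from the oral drug and from the JAK inhibitor class. The list includes "thyroid function abnormalities, lipid elevation, serum creatinine elevations, creatine phosphokinase elevations". Section 2.1 also mentions lipid abnormalities as a safety issue with oral JAK inhibitors.

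**The oral experience.** Section 2.3.2, on the Phase 2 rheumatoid arthritis study, states: "Increases in LDL, HDL, total cholesterol and triglycerides were observed". The most common adverse events, at 5% or more across the pooled SHR0302 groups up to Week 12, "included upper respiratory infection, hyperlipidemia, swollen joint, urinary tract infection, hypercholesterolemia, joint pain, and cough". The same section adds that "Mean WBC, neutrophils, lymphocyte, HGB, platelet count, serum lipid level, liver function, kidney function, and thyroid function parameters remained in the normal range" in every SHR0302 group, and that the LDL-to-HDL ratio was stable. In the methotrexate interaction study (Section 2.3.3), events after the combination included "elevated blood triglycerides, elevated aspartate aminotransferase, positive urine leukocytes and tachycardia each in 1 subject".

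**The monitoring.** Section 2.4.2 closes by naming physical examination, application site assessments, "hematology, serum chemistry, TSH, T4, urinalysis, ECG, and AE questioning", and judges these adequate for subject "safety and should detect expected AEs". Section 5.1.6 defines the laboratory content: "All tests listed in Table 3 below will be performed according to the Schedule of Visits and Assessments". It makes all samples non-fasting and lets the investigator order unscheduled tests. Section 5.1 gives similar latitude to the investigator and the sponsor.

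**The concern.** The protocol names a laboratory effect as a risk, reports it for the active ingredient, calls its monitoring adequate, and then schedules no test that would show it. A lipid rise usually has no symptoms, so physical examination, ECG and open questions about adverse events cannot be relied on to bring it out.

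Three things depend on this:

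- Change in laboratory parameters is part of the Cohort 1 primary endpoint (Protocol Section 3.2.1) and a Cohort 2 safety endpoint (SAP Section 2.2.2). For lipids there would be no scheduled data under either.
- The individual stopping rule for confirmed Grade 3 or higher laboratory abnormalities (Protocol Section 4.10) has no scheduled lipid value to act on.
- Section 2.3 describes this as the first human study of the cream. Its 12-week vehicle comparison would leave the lipid question where it stood.

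**Working it through.** The plan gives no figure on this point. The check is a cross-reference of the risk list against the panel, the schedules and the SAP.

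**Step 1. Panel content.** Table 3 has 12 serum chemistry entries: urea nitrogen, bilirubin, alkaline phosphatase, AST, ALT, albumin, sodium, potassium, chloride, glucose, creatinine and creatine kinase. Lipids among them: 0 of 12. The additional tests are TSH/T4, pregnancy tests, FSH and PK. Lipids among them: none.

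**Step 2. Risk list against panel.** I took from Section 2.4.2 the risks that are laboratory findings (the classification is mine).

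| Listed risk | Test in Table 3 |
|---|---|
| Anemia | Hemoglobin, hematocrit, red cell count |
| Lymphopenia | Differential leukocyte count |
| Neutropenia | Differential leukocyte count |
| Platelet change | Platelet count |
| Liver function | AST, ALT, bilirubin, alkaline phosphatase |
| Thyroid function | TSH, T4 |
| Creatinine | Creatinine |
| Creatine phosphokinase | Creatine kinase |
| Lipid elevation | None |
| NK cell reduction | None |

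Covered: 8 of 10. Not covered: lipids and NK cells. Raised lactic dehydrogenase, reported as an adverse event in Section 2.3.2 but not in the risk list, also has no test.

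**Step 3. Schedules.** The laboratory row in Section 1.3 covers hematology, serum chemistry, urinalysis and TSH/T4 for both cohorts, with no lipid row. SAP Tables 1 and 2 repeat it.

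**Step 4. SAP outputs.** SAP Section 9.3 summarizes hematology, chemistry (with thyroid) and urinalysis. The planned tables (SAP Section 13.1.3.5) and listings (16.2.8) add only pregnancy tests and FSH.

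**Step 5. Stated reason.** I found none in either document for leaving lipids out.

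**Step 6. Samples already planned.** In Cohort 2, chemistry is scheduled at Screening, Baseline and Weeks 4, 8 and 12, which is five time points. Screening results may serve as Baseline if the visits are within 14 days, which leaves four draws. With about 215 subjects and no dropout, that is between 215 × 4 = 860 and 215 × 5 = 1,075 chemistry samples. In Cohort 1 the points are Screening, Baseline and Days 8, 15 and 22, under the same 14-day allowance.

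**The case against.** **Potential risks are not the same as expected adverse events.** Section 2.4.2 lists the former and claims detection of the latter. Section 5.7.2 defines unexpectedness by reference to the Investigator's Brochure, which is not among these documents. The list also contains malignancy, thrombosis and gastrointestinal perforation, which have no dedicated test, so the sentence was hardly meant as one assay per risk. This stands in part. It rules out calling the sentence plainly false. It does not explain why the paragraph names a laboratory risk and then relies on a panel that omits it.

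**The lipid signal is weak for this product.** Mean lipids stayed in the normal range and the ratio was stable. The lipid finding in Section 2.3.2 comes without a dose or a placebo comparison. Section 2.4.1 puts once-daily exposure at 1.5 mg only if absorption is complete, and expects far less. Twice daily would give 2 × 1.5 = 3 mg on the same premise. Both figures lie within the 0.5 to 8 mg oral range, but only at complete absorption. This stands as a reason for a low rating. It does not single lipids out: the same section says means stayed normal for blood counts, liver, kidney and thyroid, and all of those are tested.

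**Unscheduled tests are allowed.** True, so lipid changes are not undetectable. But nothing on the schedule would prompt such a test.

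**No lipid endpoint is promised.** True. The loss is one of safety description.

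**Conclusion.** The point holds as a minor inconsistency. Lipid elevation is a listed risk with prior reports for the oral drug; 0 of 12 chemistry entries and none of the SAP laboratory outputs cover it; and no reason is given. As written, the plan yields no systematic lipid data.

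A reader might infer more than the documents support:

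- *That the monitoring as a whole is inadequate.* It is not shown to be: 8 of the 10 laboratory risks in the list have a direct test.
- *That lipids are the only laboratory signal left out.* NK cells and lactic dehydrogenase are also untested.
- *That the cream is known to raise lipids.* The evidence is from oral dosing, and mean values stayed normal.
- *That a Baseline chemistry sample will exist for all of the roughly 215 Cohort 2 subjects.* Screening results may stand in for it.

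The conclusion rests on reading serum chemistry in Section 2.4.2 as the panel in Table 3, which is the only definition that the protocol gives. No primary or secondary efficacy result is affected.

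**What to change.** Reconcile Protocol Sections 2.3.2, 2.4.2 and 5.1.6 (Table 3). Two routes would do it, and the choice belongs to the sponsor and its medical staff.

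1. **The laboratory panel covers the listed lipid risk**, using chemistry samples already scheduled. The cost is the assay on at most about 1,075 Cohort 2 samples plus those of Cohort 1, with no extra visit. The SAP's chemistry summary and shift tables repeat by parameter, so they would need no new method. The drawback is that samples are non-fasting, which makes triglycerides noisy. The protocol and SAP should also say which sample is the baseline where Screening results are reused.
2. **The statement in Section 2.4.2 is narrowed** to exclude lipids, with the reason stated. This costs a text edit. The study report would then have to say that lipids were not systematically measured.

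Under either route, a sentence on NK cell reduction would close the other gap in the same list.

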3. STUDY ENDPOINTS AND OBJECTIVES

3.1 Study Objectives

3.1.1 Primary Objectives

The objectives of this study are as follows:

Phase 1 (Cohort 1):

- To assess the safety, tolerability and PK of QD application of ARQ-252 0.3% to both hands for 2 weeks in 6 subjects with chronic hand eczema

Phase 2b (Cohort 2):

- To assess the safety and efficacy of ARQ-252 cream 0.1% QD and ARQ-252 cream 0.3% QD and BID, vs vehicle applied QD and BID for 12 weeks to subjects with chronic hand eczema

3.2 Study Endpoints

3.2.1 Primary Endpoints

Phase 1 (Cohort 1):

The primary endpoint of Cohort 1 is safety, as measured by the incidence and severity of adverse events, changes in laboratory parameters, tolerability, and pharmacokinetics.

Phase 2b (Cohort 2):

The primary endpoint of Cohort 2 is:

- The rate of an IGA score of ‘clear’ or ‘almost clear’ at Week 12

3.2.2 Secondary Endpoints

Phase 2b (Cohort 2):

The secondary endpoints of Cohort 2 are:

- The rate of achievement of IGA of ‘clear’ or ‘almost clear’ PLUS at least a 2-point improvement from Baseline at Weeks 2, 4, 8 and 12
- The rate of achievement of at least a 2-point improvement from Baseline at Weeks 2, 4, 8 and 12
- Achievement of IGA of ‘clear’ or ‘almost clear’ at Weeks 2, 4, and 8
- Time to IGA of ‘clear’ or ‘almost clear’
- Change in IGA score at Weeks 2, 4, 8, and 12 as compared to Baseline
- Change in WI-NRS pruritus score at 2 weeks, 4 weeks, 8 weeks, and 12 weeks compared to Baseline
- The rate of achievement of ≥ 4 -point reduction from Baseline in WI-NRS pruritus score at 2 weeks, 4 weeks, 8 weeks, and 12 weeks in subjects with Baseline WI-NRS pruritus score of at least 4
- Time to the first achievement of ≥ 4 -point reduction from Baseline in WI-NRS pruritus score in subjects with Baseline WI-NRS pruritus score of at least 4
- Percent change in HECSI (Hand Eczema Severity Index) score at Weeks 2, 4, 8, and 12 compared to Baseline
- Change in Pain NRS score at 2 weeks, 4 weeks, 8 weeks, and 12 weeks compared to Baseline

- The rate of achievement of ≥ 4 -point reduction from Baseline in Pain NRS score at 2 weeks, 4 weeks, 8 weeks, and 12 weeks in subjects with Baseline Pain NRS score of at least 4
- Time to the first achievement of ≥ 4 -point reduction from Baseline in Pain NRS score in subjects with Baseline Pain NRS score of at least 4
- Change from baseline in overall Quality of Life in Hand Eczema Questionnaire (QOLHEQ) score at each visit
- Percent BSA affected by disease and % change from baseline in BSA affected by disease at baseline, 2 weeks, 4 weeks, 8 weeks, and 12 weeks.

3.2.3 Exploratory Endpoints

Phase 2b (Cohort 2):

The exploratory endpoint of Cohort 2 is:

- Change from Baseline in Nail Dystrophy at each visit.

4. INVESTIGATIONAL PLAN

4.1 Overall Study Design and Plan

This is a phase 1/2b, multiple dose and 12-week, parallel group, double blind, dose ranging, vehicle-controlled study of the safety and efficacy of ARQ-252 cream 0.1% and ARQ-252 cream 0.3% in subjects with chronic hand eczema.

There are 2 cohorts of subjects:

- Cohort 1 is a multiple dose cohort in which subjects with chronic hand eczema will be assigned to ARQ-252 cream 0.3% QD x 2 weeks to be applied to both hands. PK and tolerability will be evaluated.
- Cohort 2 is a parallel group, double blind, vehicle-controlled cohort in which subjects with chronic hand eczema will be randomized to ARQ-252 cream 0.3% QD, ARQ-252 cream 0.3% BID, ARQ-252 cream 0.1% QD, vehicle cream BID or vehicle cream QD x 12 weeks to be applied to both hands. Safety and efficacy will be evaluated.

